## **Data collection and Outcome Measures**

The demographic data of the participants includes age, gender, diagnosis, procedure, and ASA class (ASA Physical Status Classification 2014). Further patient data will be collected by 1) The Good Perioperative Nursing Care Scale (Leinonen & Leino-Kilpi 2001) measuring the quality of perioperative care; 2) 15D instrument measuring the health-related quality of life among adults (Sintonen 2001) and 3) STAI, the State-Trait Anxiety Inventory; measuring anxiety in adults (Spielberger et al. 2010). The schedule for patient data collection is presented in Table 1.

**Table 1.** Schedule of patient data collection

Instrument	Baseline (preoperative visit 2-3 weeks prior to surgery)	Cross-section (at discharge)	Post-test (three months after discharge)
15 D	x		x
STAI	x		x

Good Perioperative Nursing Care Scale		x	
---------------------------------------	--	---	--

### **Primary Outcome Measures**

1. Change from baseline Health Related Quality of Life (HRQoL) at three months after the surgical procedure. Time Frame: Baseline 2-3 weeks prior to, and post-measurement 3 months after the procedure (The 15D instrument)

### **Secondary Outcome Measures**

1. Change from baseline Surgery-related anxiety at three months after the surgical procedure. Time frame: Baseline 2-3 weeks prior to, and post-measurement 3 months after the procedure (The State-Trait Anxiety Inventory (STAI))
2. Quality of perioperative care as experienced by surgical patients. Time frame: On average the third postoperative day, depending the time of discharge (Good Perioperative Nursing Care Scale)

### **Ethical considerations**

The ethical codes and good scientific practice (TENK 2012) will be followed throughout the research. Participants will get written and oral information about the study, and a written informed consent will be asked. The participants will be informed about their right to decline from the study at any time, and they are told that this will not affect their care in any way. They also have the right to withdraw their consent in which case their data will not be used in the study. This clinical trial has been approved by the Operative (surgical) Ethical Committee of Helsinki University Hospital (decision number §16/27.7.2016). Permissions to use instruments (15D, STAI, Good Perioperative Nursing Care Scale) have been asked from the copyright holders.

**Statistical Analysis Plan:**

Descriptive statistics will be used to present characteristics of the study participants. One- and multi-way analysis of variance will be used to compare means of groups. Interaction terms will be used to compare means of the groups defined by combinations of categorical independents. Tukey's adjustment will be used to account for multiple comparison if necessary. Statistical significance of dependencies between categorical variables are tested using Chi-square tests. SAS® statistical software, version 9.4 (SAS Institute Inc., Cary, NC, USA) will be used in statistical analysis.

In the analysis of the patient data, collected with the GPNCS, if a respondent answers to less than 50% of the quality statements, his or her response will be excluded from the analysis. Frequencies and percentages obtained with the Pearson chi-square test are calculated for the background data. Non-parametric tests are used when comparing background factors with quality categories. The reliability of the scale is checked with a Cronbach's alpha coefficient. In the analysis of data sets, the non-parametric tests will include the Kruskall-Wallis test and Mann Whitney U-test with Bonferroni corrections. A *p*-value of 0.05 is considered statistically significant.

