#### **Study sample and setting**

The study will be conducted at the Helsinki University Hospital; more specifically at the operating department K of the Peijas Hospital. The study population consist of adult female and male patients scheduled for either total hip arthroplasty (THA) or total knee arthroplasty (TKA). A control group and an experimental (intervention) group will be formed. The participants are recruited at their preoperative visits to the outpatient clinic two to three weeks prior to their scheduled operations. The inclusion criteria: 18 years of age or older, able to comprehend the study information and complete the questionnaires, and operation being performed under spinal anesthesia. One exclusion criterion for the intervention group is that the planned surgery is performed on Friday, because the postoperative visits cannot be performed during the weekend.

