## **Randomization and sample size**

Randomization of participants is performed by independent third parties (two nurse assistants at the outpatient clinic). All patients scheduled for THA and TKA attending the outpatient clinic are considered eligible and invited to participate in randomization if they meet the inclusion criteria. Eligible patients will draw one of two cards; one indicate an invitation to participate the study and the other is blank, indicating no participation in the study. Patients in the control group will be recruited every other week and patients for the intervention group every week between. This pattern will be repeated until the desired number of patients are recruited. This stratification will ensure that patients in different groups do not exchange information in the postoperative ward. The sample size requirement for comparing two means was checked with power analysis (2-sided test) with  $\alpha = 0.05$ ,  $\beta = 0.9$ , standard deviation 0.08, and differences of means 0.03 in 15D scores, which is within the slight difference of 0.015-0.035 (Alanne, Roine, Räsänen, Vainiola, & Sintonen, 2015). A sufficient sample size is determined to be 152 per group.

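### The SAP assigns no model to the primary 15D outcome and does not use the collected baseline 15D as a covariate; a prespecified ANCOVA would usually be more precise

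*Combined protocol and SAP*

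**What the plan says.** The protocol has one primary outcome, under Primary Outcome Measures: "Change from baseline Health Related Quality of Life (HRQoL) at three months after the surgical procedure". Its time frame is "Baseline 2-3 weeks prior to, and post-measurement 3 months after the procedure (The 15D instrument". Table 1, under Data collection and Outcome Measures, schedules both 15D and STAI at baseline and at three months, so the baseline score will be in hand for both.

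The Statistical Analysis Plan is two paragraphs long. On means it says that "One- and multi-way analysis of variance will be used to compare means of groups" and that "Interaction terms will be used to compare means of the groups defined by combinations of categorical independents". It also lists chi-square tests and, mainly for the nursing-care scale, non-parametric tests. It names no continuous covariate, and no sentence ties a model to 15D.

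Under Randomization and sample size, the calculation uses "standard deviation 0.08, and differences of means 0.03 in 15D scores", a two-sided 5% level and a printed β of 0.9, and arrives at 152 per group. It does not say whether the SD is that of a 15D score or of the change in score. On group formation, the same section says: "Patients in the control group will be recruited every other week and patients for the intervention group every week between". Under Study sample and setting: "One exclusion criterion for the intervention group is that the planned surgery is performed on Friday".

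**The concern.** A baseline measurement of the primary outcome is taken, but on the SAP's wording it can enter only through the subtraction that defines change, or perhaps through a time factor. Subtraction fixes the baseline slope at 1. Unless the true slope is close to 1, the group comparison then carries noise that could be removed at no data cost, and its confidence interval is wider than it needs to be.

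The second matter is prespecification. If the groups differ at baseline, a change-score analysis and a baseline-adjusted analysis give different estimates. With no model assigned to 15D, the choice between them could be made after both results are known. Recruitment by alternating week, and a Friday exclusion stated for one group only, mean that a baseline difference cannot be assumed to be chance.

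**Working it through.** **Inputs from the documents.** Difference 0.03, SD 0.08, two-sided 5% level, 152 per group (Randomization and sample size). The printed β = 0.9 is read as power 0.9, because only that reading gives the stated size.

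**Inputs assumed.** r, the correlation between baseline and three-month 15D, taken as 0.3, 0.5, 0.7 and 0.8; and k, the three-month SD divided by the baseline SD, taken as 0.8, 1 and 1.25. The documents give neither.

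**Step 1: the plan's own figure.** n = 2 × (0.08 × (1.960 + 1.282) / 0.03)² = 149.4, so 150 per group, or 151 with the t distribution. At 152 per group, t-based power is 90.3%. The plan's 152 is reproduced.

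**Step 2: relative precision.** With baseline SD s and three-month SD ks:

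- variance of change = s²(1 + k² − 2kr)
- ANCOVA residual variance = k²s²(1 − r²)
- ratio = k²(1 − r²) / (1 + k² − 2kr)

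At k = 1 the ratio is (1 + r)/2. It never exceeds 1, and equals 1 only when kr = 1, that is, when the baseline slope is 1.

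| k | r = 0.3 | r = 0.5 | r = 0.7 | r = 0.8 |
|---|---|---|---|---|
| 0.8 | 0.50 | 0.57 | 0.63 | 0.64 |
| 1 | 0.65 | 0.75 | 0.85 | 0.90 |
| 1.25 | 0.78 | 0.89 | 0.98 | 1.00 |

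**Step 3: power at 152 per group, k = 1.** Noncentral t, with one degree of freedom fewer for ANCOVA. The two readings of 0.08 are kept apart.

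*Reading A, 0.08 is the SD of change.* ANCOVA SD = 0.08 × √ratio.

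*Reading B, 0.08 is the SD of the score at both times.* SD of change = 0.08 × √(2 − 2r); ANCOVA SD = 0.08 × √(1 − r²).

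| | r = 0.3 | r = 0.5 | r = 0.7 | r = 0.8 |
|---|---|---|---|---|
| A, change score | 90.3% | 90.3% | 90.3% | 90.3% |
| A, ANCOVA | 98.1% | 96.4% | 94.2% | 93.0% |
| B, change score | 78.6% | 90.3% | 98.8% | 99.9% |
| B, ANCOVA | 92.7% | 96.4% | 99.5% | 99.97% |

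Under reading A the 95% CI half-width is 0.0181 for the change score, against 0.0146 / 0.0156 / 0.0166 / 0.0171 for ANCOVA. At k = 1.25 and r = 0.7 the gain nearly vanishes (half-width 0.0179, power 90.8%).

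**Step 4: how far the two estimates can part.** They differ by (1 − kr) times the baseline difference. Take a baseline difference of one standard error, baseline SD × √(2/152), at k = 1. Under reading A the baseline SD is 0.08/√(2 − 2r), which is 0.068 / 0.080 / 0.103 / 0.126. Under reading B it is 0.08, so the standard error is 0.0092.

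| Gap | r = 0.3 | r = 0.5 | r = 0.7 | r = 0.8 |
|---|---|---|---|---|
| A | 0.0054 | 0.0046 | 0.0036 | 0.0029 |
| B | 0.0064 | 0.0046 | 0.0028 | 0.0018 |

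Against the 0.03 target these are about 18 / 15 / 12 / 10% under A and 21 / 15 / 9 / 6% under B. One standard error is a chance-sized difference. The documents give nothing from which to size a systematic one.

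Steps 2 and 3 assume no systematic baseline difference between groups. Step 3 also assumes independent patients and 152 completers per group, so the ratios in step 2 are firmer than the absolute powers.

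**The case against.** The strongest reply is that nothing in the plan is wrong. Defining the outcome as change already uses the baseline score, a change-score ANOVA is valid when baseline differences are chance, and under reading A it already has the planned 90% power. The gain from ANCOVA depends on two quantities that the documents do not give, and at one corner of the grid it is nil. All of this stands. It makes the point one of missed precision and incomplete specification, not of error. It does not remove the point, since on these formulas the adjusted analysis loses nothing beyond one degree of freedom.

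It is also fair to say that the sentence on analysis of variance is general and names no outcome, so its application to 15D is inferred. A reader should not conclude that the SAP has committed itself to an unadjusted analysis of 15D. What it lacks is any commitment, and that itself needs repair.

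The allocation argument has limits too. A reader might infer that alternating weeks and the Friday exclusion bias the change-score result and that ANCOVA would put this right. The documents do not support either step. They give no link between recruitment week or day of surgery and baseline 15D, and if the groups do differ systematically, neither estimate is automatically unbiased. Allocation is therefore a reason to name one analysis in advance. The reason to choose ANCOVA is precision.

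**Conclusion.** The point holds as a gap in specification with a likely loss of precision. The SAP should name the 15D analysis, and ANCOVA on baseline 15D is the better choice. Over the assumed range its variance is 0.50 to 1.00 of that of the change score, and 0.65 to 0.90 with equal SDs.

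A reader might infer that 152 per group is too few, particularly from the 78.6% under reading B at r = 0.3. That does not follow. The figure needs one reading of an ambiguous SD together with an assumed low correlation, and the stated size reproduces from the stated inputs. It does show that ANCOVA keeps power above 90% on either reading throughout the k = 1 range, whereas the change score does not.

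Confidence is medium, because r and k are assumed and the use of ANOVA for 15D is inferred. Any clustering by week is a separate matter that these figures leave out and that baseline adjustment does not address.

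**What to change.** State the primary analysis as ANCOVA of three-month 15D on group and baseline 15D, reporting the adjusted group difference with its 95% CI. Taking change in 15D as the response with the same covariate gives an identical group estimate, because subtracting baseline alters only the baseline coefficient. The endpoint as defined therefore need not change. Procedure (hip or knee) may be added as a prespecified factor if wanted. Report the unadjusted change-score comparison as a sensitivity analysis, and use the same form for three-month STAI with baseline STAI.

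The cost is SAP wording, one degree of freedom per covariate and one extra sensitivity analysis. No new data are needed, since both baselines are already scheduled.

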## **Study Protocol:**

### **Background**

Earlier research findings show that when a caring encounter is established where the nurse informs the patient about the perioperative process and its proceedings and educates the patient, a significant impact on both postoperative pain and the recovery from surgery can be achieved (Bager et al. 2015, Bailey 2015, Johansson et al. 2014). Also, anxiety increases the postoperative pain and slows down the recovery from surgery (Marks 2015). An earlier investigation comparing recovery of general surgery patients to orthopedic patients showed that overall, the orthopedic patients were less recovered in the acute recovery phase as well as after one month postoperatively. The most common reason for slow recovery was pain, which was ranked high in the acute recovery phase for both orthopedic and general surgery patients. The authors state that support for the orthopedic patients must be improved (Forsberg et al. 2015).

An investigation conducted by McHugh et al. (2013) revealed that patients experience improvement in psychosocial and biomedical outcomes at six months after hip replacement. The strongest predictors of recovery were anxiety and depression, pain, previous joint surgery and taking pain medication. By recognizing these factors nurses are able to identify and provide more support for patients at risk of poor recovery after hip replacement.

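### The SAP plans no use of baseline anxiety (STAI) as a continuous covariate in the 15D comparison, although the protocol names anxiety as a predictor of recovery and measures it at baseline

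*Combined protocol and SAP*

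**What the plan says.** The Statistical Analysis Plan gives one family of methods for means: "One- and multi-way analysis of variance will be used to compare means of groups". The next sentence, on interaction terms, refers to categorical independents. Analysis of covariance, regression and continuous covariates appear nowhere. The other tests named (chi-square, Kruskal-Wallis, Mann-Whitney) do not adjust for a continuous score. The SAP does not say which factors enter the 15D analysis.

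The Background reports from a cited hip replacement study: "The strongest predictors of recovery were anxiety and depression, pain, previous joint surgery and taking pain medication". Data collection and Outcome Measures lists "STAI, the State-Trait Anxiety Inventory; measuring anxiety in adults", and Table 1 schedules it at baseline and at three months. Age is recorded as demographic data. The only stated use of baseline STAI is in its own change score, a secondary outcome. The primary outcome is the change in 15D from baseline to three months.

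On group formation, Randomization and sample size states: "Patients in the control group will be recruited every other week and patients for the intervention group every week between". The cards that patients draw decide whether they are invited, not which arm they join. Under Study sample and setting, Friday surgery is an exclusion for the intervention group only.

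**The concern.** The protocol names a prognostic factor and measures it as a continuous score before surgery, but plans an analysis with no place for it in that form. Within a multi-way ANOVA, STAI could enter only after being cut into groups, and no cut-points are given, so they would be chosen after the data are in.

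Two things are at stake. One is precision: a covariate related to the outcome narrows the confidence interval. The other is bias: with arms set by recruitment week and an exclusion that applies to one arm only, balance on baseline anxiety is not assured, and an imbalance could carry into the 15D difference.

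**Working it through.** **Inputs from the documents.** Two-sided alpha 0.05; "standard deviation 0.08, and differences of means 0.03 in 15D scores"; "A sufficient sample size is determined to be 152 per group". The plan writes beta = 0.9, read here as power 0.90. Taken literally it would give 7 per group.

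**Inputs assumed.** Correlation r between the covariate and the analysed 15D outcome: 0.1 to 0.5. Baseline STAI imbalance d: 0.2 to 0.3 SD. The documents give neither.

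**1. The plan's own figure.** n = 2 × [SD × (z₀.₉₇₅ + z₀.₉₀) / Δ]² = 2 × [0.08 × (1.960 + 1.282) / 0.03]² = 149.4, so 150 per group. The t-based version gives 150.4, so 151. The stated 152 is reproduced within two patients. It is an unadjusted comparison of two means, with power 90.5% at 152 per group (90.3% t-based). The sample size is not in error; it assumes no covariate.

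**2. Precision.** With a continuous covariate, SD becomes 0.08 × √(1 − r²).

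| r | Variance reduction (r²) | n per group for 90% power | Power at 152 per group |
|---|---|---|---|
| 0 | 0% | 150 | 90.5% |
| 0.1 | 1% | 148 | 90.8% |
| 0.2 | 4% | 144 | 91.6% |
| 0.3 | 9% | 136 | 92.9% |
| 0.4 | 16% | 126 | 94.6% |
| 0.5 | 25% | 113 | 96.5% |

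At r = 0.3 the confidence interval shortens by 1 − √0.91 = 4.6%. For illustration only, since the SAP proposes no cut: a median split of a normal covariate keeps 64% of the explained variance, giving n = 141 and power 92.0% at r = 0.3.

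**3. Bias from an imbalance.** The endpoint is a change, so only STAI's association with change matters. If 0.08 is the SD of change, the shift is d × 0.08 × r(change). If 0.08 is the SD of 15D at each visit, the shift is d × 0.08 × (difference between the correlations at the two visits). Absolute values:

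- Correlation 0.4 at both visits: 0.3 × 0.08 × 0 = 0.
- Correlations 0.4 and 0.3, d = 0.3: 0.3 × 0.08 × 0.1 = 0.0024, or 8% of 0.03.
- Correlation with change 0.2, d = 0.2: 0.2 × 0.08 × 0.2 = 0.0032, or 11%.
- Correlation with change 0.4, d = 0.3: 0.3 × 0.08 × 0.4 = 0.0096, or 32%. At a correlation of 0.5 it would be 0.012.

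The standard error of the difference is 0.08 × √(2/152) = 0.0092. With no true effect, the rejection rate is Φ(−1.96 + b/SE) + Φ(−1.96 − b/SE): 5.8% for b = 0.0024 and 18% for b = 0.0096.

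**4. Plausibility of the imbalance.** With individual randomization at 152 per group, the standardized difference has SE √(2/152) = 0.115. Then 0.2 SD or more in either direction occurs about 8% of the time, and 0.3 SD or more about 0.9%. Alternating weeks carry no such guarantee, but the documents give no mechanism that would shift anxiety between weeks.

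**The case against.** The case for leaving the plan alone has several sound parts.

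- **The change score already removes some of the problem.** Anxiety that lowers 15D equally before and after surgery cancels. This stands, and it is why the range in step 3 starts at zero.
- **The prognostic evidence is indirect.** It comes from one cited hip replacement study, with outcomes at six months, and it names anxiety and depression jointly. It does not show that STAI predicts 15D change at three months in hip and knee patients. This stands.
- **The precision gain is small.** At r = 0.3 it is 2.4 percentage points of power, from a plan that already reaches 90%. This stands. STAI's contribution once baseline 15D is in the model may be smaller still and cannot be computed from the documents.
- **The SAP does not forbid covariates.** A reader might infer that STAI and age cannot enter the analysis. The text does not support that: the reference to categorical independents sits in the sentence on interaction terms, and the named software fits covariates. What can be said is that none is planned. That still matters, because a covariate chosen after the data are seen is open to challenge.

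A reader might also infer that type I error is inflated to 17% or 18%. That requires a systematic 0.3 SD imbalance together with a correlation of 0.4 with change, and neither figure has support in the documents. Nor do they support giving age equal standing: it is collected, but the Background does not name it as a predictor.

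**Conclusion.** The point holds as a modest, inexpensive improvement to the analysis. The SAP makes no planned use of baseline STAI as a continuous covariate for 15D, although the protocol gives its own reason to use it and the allocation by week does not assure balance. It does not show that the planned comparison is biased or that the sample size is wrong.

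Under the assumed correlations of 0.1 to 0.5, adjustment reduces variance by 1% to 25%. Under an assumed imbalance of 0.2 to 0.3 SD, the unadjusted shift in 15D change runs from about 0 to about 0.01 against a target of 0.03. The upper end needs both the larger imbalance and a correlation with change of about 0.4. Adjustment would remove the linear part of a measured anxiety difference. It would not make alternating weeks equivalent to individual randomization.

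**What to change.** Replace the general ANOVA statement, for the primary outcome, with a prespecified general linear model (analysis of covariance):

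- Outcome: 15D at three months.
- Factors: group, and procedure (hip or knee arthroplasty).
- Continuous covariates: baseline 15D and one named baseline STAI score. The instrument has state and trait parts, so the SAP must say which is used.
- Optional: age as a continuous term, declared in advance.

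Neither STAI nor age should be categorized for this purpose. With baseline 15D in the model, the group effect is the same whether the outcome is the three-month value or the change, so the primary endpoint is kept. The SAP should also state how a missing baseline score is handled, for example by a simple imputation from pooled baseline data that ignores the arm.

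The cost is one SAP sentence, three or four degrees of freedom out of about 300, and the rule for missing baseline scores. All the data are already collected, and 152 per group can stay.

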### **Aim and objectives**

The aim of this study is to improve the surgical patients' care process. The objective is to explore the effect of a new perioperative practice model on 1) patient outcomes (satisfaction, surgery-related anxiety and quality of life), 2) nursing outcomes (organizational engagement), and 3) organization outcomes (timeline of surgical care process).

The study is part of [name] doc research project "Knowledge-based management in perioperative nursing". At the same time it links to professor [name]'s research projects concerning the Perioperative Dialogue.

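### The SAP's GPNCS paragraph names neither the intervention-control comparison nor the tests that share Bonferroni; specify one adjusted arm comparison, with Holm across the quality categories

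*Combined protocol and SAP*

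**What the plan says.** The protocol (Aim and objectives) states: "The objective is to explore the effect of a new perioperative practice model on 1) patient outcomes (satisfaction, surgery-related anxiety and quality of life"). Under Secondary Outcome Measures, item 2 is "Quality of perioperative care as experienced by surgical patients", measured with the GPNCS around discharge. In Table 1 it is the only one of the three patient instruments scheduled at that time; the 15D and the STAI are taken at baseline and three months after discharge.

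The SAP has two paragraphs. The first is general: "One- and multi-way analysis of variance will be used to compare means of groups", followed by interaction terms and "Tukey's adjustment will be used to account for multiple comparison if necessary". It is tied to no particular outcome.

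The second is about the GPNCS. It sets a 50% response rule, chi-square tests for background data and Cronbach's alpha. On comparisons it says: "Non-parametric tests are used when comparing background factors with quality categories". It then adds: "In the analysis of data sets, the non-parametric tests will include the Kruskall-Wallis test and Mann Whitney U-test with Bonferroni corrections". It ends with the threshold: a p-"value of 0.05 is considered statistically significant".

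**The concern.** A reader who follows the GPNCS paragraph literally learns which kinds of patients rate their care higher. That is not the question behind secondary outcome 2, which is whether the new model changes the rating. Four decisions that the SAP should settle are left open:

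- whether the arm comparison uses a total score or each quality category;
- whether it uses ANOVA or a rank test;
- which tests share the Bonferroni correction;
- whether 0.05 applies before or after that correction.

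These choices could then be made after the data are seen.

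The listed rank tests also make no use of baseline data. That matters here because the arms are formed by alternating weeks (Randomization and sample size), while the card draw only decides whether a patient is invited. Patients with Friday surgery are excluded from the intervention group only (Study sample and setting). The arms may therefore differ at baseline more than individually randomised arms would.

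**Working it through.** **1. What the text covers.** The objective and secondary outcome 2 call for intervention against control on the GPNCS. The GPNCS paragraph names background factors against quality categories. It does not define background factors; the nearest list is the demographic data under Data collection and Outcome Measures (age, gender, diagnosis, procedure, ASA class), which does not include study arm. The sentence listing the rank tests is not limited to background factors, and Mann-Whitney is a two-sample test. The general ANOVA sentence excludes no outcome. So the arm comparison is possible under the SAP but is not specified.

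**2. The plan's own figure.** The only calculated figure is for the 15D (two-sided alpha 0.05, SD 0.08, difference 0.03, and 0.9 read as power).

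n per group = 2 × (1.960 + 1.282)² × (0.08/0.03)² ≈ 149.4, so 150.

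The plan gives 152, which agrees. Power at 152 is Φ(0.375 × √(152/2) − 1.960) = Φ(1.309) = 0.905. This does not bear on the GPNCS directly, for which no effect size, SD or number of tests is given.

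**3. Illustration for the GPNCS.** Assumptions, none of them a GPNCS figure from the documents:

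- shift of 0.03/0.08 = 0.375 SD, borrowed from the 15D;
- 152 per group, with Mann-Whitney efficiency 0.955, so effective n = 152 × 0.955 = 145.2;
- K = 5 to 8 quality categories;
- five background factors, taken from the demographic list.

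Non-centrality = 0.375 × √(145.2/2) = 3.195. Power with m tests under Bonferroni = Φ(3.195 − z), where z is the two-sided critical value at 0.05/m.

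| Family | m | alpha | z | Power per category |
|---|---|---|---|---|
| one test | 1 | 0.05 | 1.960 | 0.89 |
| arm comparisons, K = 5 | 5 | 0.01 | 2.576 | 0.73 |
| arm comparisons, K = 8 | 8 | 0.00625 | 2.734 | 0.68 |
| arm plus five factors, K = 5 | 5 × 6 = 30 | 0.00167 | 3.144 | 0.52 |
| arm plus five factors, K = 8 | 8 × 6 = 48 | 0.00104 | 3.279 | 0.47 |

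**4. Holm against Bonferroni over the K arm comparisons** (simulation, correlations between categories 0.3 and 0.6).

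- One category shifted: 0.73/0.73 at K = 5, 0.69/0.69 at K = 7, 0.68/0.68 at K = 8 (Bonferroni/Holm). The gain is about nil.
- Two categories shifted: gain about 0.01 to 0.02.
- All categories shifted: Holm reaches about 0.78 to 0.84, a gain of about 0.09 to 0.12.

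Holm controls the family-wise error under the same conditions as Bonferroni and rejects whenever Bonferroni does.

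**The case against.** The strongest reply is that the SAP does plan a group comparison. The protocol uses the word group for the study arms, ANOVA of group means is stated without restriction, and Mann-Whitney suits two arms. This largely stands. A reader might infer that the GPNCS will be tested on the wrong question, but that is an inference from silence. What remains is that the general paragraph also uses groups for combinations of categorical factors. If both paragraphs apply to the GPNCS, it has two tests and two multiplicity rules (Tukey and Bonferroni), with nothing to say which decides.

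A reader might also infer that the test will be run at the wrong level, or with inflated error. The documents do not support this. The family is unstated, the rank-test sentence carries a correction ("the non-parametric tests will include the Kruskall-Wallis test and Mann Whitney U-test with Bonferroni corrections"), and a broad family makes the arm comparison more conservative. Uncorrected testing over several categories would arise only on another reading, such as ANOVA category by category.

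It is also fair to say that the objective is worded as exploratory, that the GPNCS is secondary, and that the power figures rest on borrowed inputs. A formal confirmatory family is therefore a choice. But the SAP has already chosen to correct for multiplicity, so it should say over what, and Holm does that at no loss against Bonferroni.

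**Conclusion.** The concern holds as a gap in specification, with two improvements to the stated method. The GPNCS paragraph does not name the intervention-control comparison that the objective and secondary outcome 2 require, and it does not define the Bonferroni family. The listed rank tests also leave unused the baseline data that would help when arms alternate by week.

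The size is uncertain. If the assumed inputs applied, pooling background-factor tests with the arm comparisons would lower power per category from 0.73 to 0.52 (K = 5) or from 0.68 to 0.47 (K = 8). No passage states such pooling. The gain from Holm depends on how many categories the intervention moves, and is negligible if it moves only one.

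**What to change.** Amend the GPNCS paragraph of the SAP to state:

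- The comparison of interest is intervention against control for each quality category.
- One primary analysis is used, adjusted for baseline data already collected, for example procedure, age, gender, ASA class and baseline STAI. It can be a proportional-odds model or, if category scores are near continuous, the multi-way ANOVA already planned. The choice is fixed before the data are seen.
- A Mann-Whitney test stratified by procedure is the sensitivity analysis.
- Holm replaces Bonferroni, across the arm comparisons only, and 0.05 applies to the Holm-adjusted p-values.
- Comparisons of background factors with quality categories are descriptive and lie outside that family.

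The cost is wording; no new data are needed. Background-factor associations lose their significance claim, and the adjusted model needs its assumptions checked (proportional odds, or residuals for ANOVA). Adjustment for measured baseline data reduces, but cannot remove, differences that come from allocating by week, and it does not by itself allow for patients in the same week being alike.
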